Indicator of pelvic infection/abscess	CRF-9, CRF-11,	Binary	surgery through last visit	Through the timepoint of follow-up, based on the systematic collection of open-ended adverse events as reported on the AE log with an onset start date on or after the date of surgical intervention and based on the specific

		1		
	CRF-13, AE log			complications as reported on the hospitalization CRF-9, coordinator post- operative CRF-11, and coordinator follow-up CRF-13 collected during hospitalization, at 6-weeks, and in 6-month intervals through 5 years respectively, the indicator is defined as follows:
				1 = Yes, if pelvic infection/abscess is reported as evident (i.e. response of "AE", "SAE") on any of the complication tables as described above or on the AE log identified by the AE verbatim terms containing "pelvic infection", "pelvic abscess" (case insensitive)
				0 = No, else if subject attended at least one post-operative visit immediately following surgical intervention or after and complication(s) of interest specified above are reported as "Not Evident" across all attended post-operative visits. Subjects with missing responses are included as long as the subject has at least one "Not Evident" response (assuming low missing response rate among attended visits). . = Missing, otherwise
Indicator of urinary tract infections (UTI)	CRF-9, CRF-11, CRF-13, AE log	Binary	surgery through last visit	Through the timepoint of follow-up, based on the systematic collection of open-ended adverse events as reported on the AE log with an onset start date on or after the date of surgical intervention and based on the specific complications as reported on the hospitalization CRF-9, coordinator post-operative CRF-11, and coordinator follow-up CRF-13 collected during hospitalization, at 6-weeks, and in 6-month intervals through 5 years respectively, the indicator is defined as follows:
				1 = Yes, if lower urinary tract infection is reported as evident (i.e. response of "AE", "SAE") on any of the complication tables as described above or on the AE log identified by the MedDRA coded preferred term "urinary tract infection" (case insensitive)
				0 = No, else if subject attended at least one post-operative visit immediately following surgical intervention or after and

				
 
complication(s) of interest specified above are reported as "Not Evident" across all attended post-operative visits. Subjects with missing responses are included as long as the subject has at least one "Not Evident" response (assuming low missing response rate among attended visits).
 
. = Missing, otherwise
 

Indicator of vaginal infection or atypical vaginal discharge after 12 weeks	CRF-13, AE log	Binary	after 12 weeks through last visit	Through the timepoint of follow-up, based on the systematic collection of open-ended adverse events as reported on the AE log with an onset start date 12 weeks after the date of surgical intervention and based on the specific complications as reported on the coordinator follow-up CRF-13 collected in 6-month intervals through 5 years respectively, the indicator is defined as follows:
				1 = Yes, if vaginal infection or atypical/vaginal discharge is reported as evident (i.e. response of "AE", "SAE") on any of the complication tables as described above or on the AE log identified by the MedDRA coded preferred terms "vaginal infection", "vulvovaginal mycotic infection", "bacterial vaginosis" (case insensitive) and other adverse events as determined during masked review. Masked review identified no further terms.
				0 = No, else if subject attended at least one post-operative visit immediately following surgical intervention or after and complication(s) of interest specified above are reported as "Not Evident" across all attended post-operative visits. Subjects with missing responses are included as long as the subject has at least one "Not Evident" response (assuming low missing response rate among attended visits).
				. = Missing, otherwise
				*Note: During masked review prior to final database lock, a listing of all adverse events on the AE log will be generated with AE verbatim terms mapped to a MedDRA coded preferred term and system organ class and

				manually reviewed by a clinical investigator to identify all AEs that may be a vaginal infection or atypical vaginal discharge. These AEs will be identified either by their MedDRA coded preferred term(s) or the verbatim term(s). If needed, a detailed listing of the manually identified AEs will be generated with details from the AE log including onset date, end date, grade, attribution, serious indicator, outcome, and comments and manually reviewed by a clinical investigator to identify all AEs that are a vaginal infection or an atypical vaginal discharge.
Indicator of vaginal bleeding after 12 weeks	CRF-13, AE log	Binary	after 12 weeks through last visit	Through the timepoint of follow-up, based on the systematic collection of open-ended adverse events as reported on the AE log with an onset start date 12 weeks after the date of surgical intervention and based on the specific complications as reported on the coordinator follow-up CRF-13 collected in 6-month intervals through 5 years respectively, the indicator is defined as follows:
				1 = Yes, if denovo vaginal bleeding is reported as evident (i.e. response of "AE", "SAE") on any of the complication tables as described above or on the AE log identified by the MedDRA coded preferred term "vaginal haemorrhage" (case insensitive)
				0 = No, else if subject attended at least one post-operative visit 6 months or after and complication(s) of interest specified above are reported as "Not Evident" across all attended post-operative visits. Subjects with missing responses are included as long as the subject has at least one "Not Evident" response (assuming low missing response rate among attended visits).
				. = Missing, otherwise
Indicator of fistula formation	CRF-9, CRF-11, CRF-13, AE log	Binary	surgery through last visit	Through the timepoint of follow-up, based on the systematic collection of open-ended adverse events as reported on the AE log with an onset start date on or after the date of surgical intervention and based on the specific complications as reported on the hospitalization CRF-9, coordinator post-operative CRF-11, and coordinator follow-up CRF-13 collected during

				hospitalization, at 6-weeks, and in 6-month intervals through 5 years respectively, the indicator is defined as follows:
				1 = Yes, if vesicovaginal fistula, rectovaginal fistula, ureterovaginal fistula, urethrovaginal fistula, enterovaginal/colovaginal fistula, or enterovesical fistula is reported as evident (i.e. response of "AE", "SAE") on any of the complication tables as described above or on the AE log identified by the AE verbatim terms containing "vesicovaginal fistula", "rectovaginal fistula", "ureterovaginal fistula", "urethrovaginal fistula", "enterovaginal fistula", "enterovesical fistula" (case insensitive)
				
 
0 = No, else if subject attended at least one post-operative visit immediately following surgical intervention or after and complication(s) of interest specified above are reported as "Not Evident" across all attended post-operative visits. Subjects with missing responses are included as long as the subject has at least one "Not Evident" response (assuming low missing response rate among attended visits).
 
. = Missing, otherwise
 

Indicator of neuromuscular disorder	CRF-8, CRF-9, CRF-11, CRF-13, AE log, (CRF-10)	Binary	surgery through last visit	Through the timepoint of follow-up, based on the systematic collection of open-ended adverse events as reported on the AE log with an onset start date on or after the date of surgical intervention and based on the specific complications as reported on the surgeon's report (unblinded) CRF-8, hospitalization CRF-9, coordinator post-operative CRF-11, and coordinator follow-up CRF-13 collected during surgery, during hospitalization, at 6-weeks, and in 6-month intervals through 5 years respectively, the indicator is defined as follows:
				1 = Yes, if neuromuscular disorder is reported as evident (i.e. response of "AE", "SAE") on any of the complication tables as described above or on the AE log identified by the MedDRA coded preferred terms "neuromyopathy" ,

				"sciatica", "spondylitic myelopathy" (case insensitive) and other adverse events as determined during masked review. Masked review identified free-text other specify complication fields containing "sciatic pain" (case insensitive) on any of the complication tables as described above or on CRF-10 collected at 6-weeks and in 6-month intervals through 5 years.
				0 = No, else if subject attended at least one post-operative visit immediately following surgical intervention or after and complication(s) of interest specified above are reported as "Not Evident" across all attended post-operative visits. Subjects with missing responses are included as long as the subject has at least one "Not Evident" response (assuming low missing response rate among attended visits).
				. = Missing, otherwise
				*Note: During masked review prior to final database lock, a listing of all adverse events on the AE log will be generated with AE verbatim terms mapped to a MedDRA coded preferred term and system organ class and manually reviewed by a clinical investigator to identify all AEs that may be a neuromuscular disorder. These AEs will be identified either by their MedDRA coded preferred term(s) or the verbatim term(s). If needed, a detailed listing of the manually identified AEs will be generated with details from the AE log including onset date, end date, grade, attribution, serious indicator, outcome, and comments and manually reviewed by a clinical investigator to identify all AEs that are a neuromuscular disorder.
Indicator of vaginal scarring after 12 weeks	CRF-10, AE log	Binary	after 12 weeks through last visit	Through the timepoint of follow-up, based on the systematic collection of open-ended adverse events as reported on the AE log with an onset start date 12 weeks after the date of surgical intervention and based on the specific complications as reported on the evaluator (blinded) follow-up CRF-10 collected at 6-weeks and in 6-month intervals through 5 years, the indicator is defined as follows:

				1 = Yes, if vaginal scarring is reported as evident (i.e. response of "A F" "C A F") are served as evident (i.e. response of
				"AE", "SAE") on any of the complication tables as described above or on the AE log identified by the MedDRA coded preferred term "vulvovaginal injury" (case insensitive) and the AE verbatim term containing "scar" (case insensitive)
				0 = No, else if subject attended at least one post-operative visit 6 months or after and complication(s) of interest specified above are reported as "Not Evident" across all attended post-operative visits. Subjects with missing responses are included as long as the subject has at least one "Not Evident" response (assuming low missing response rate among attended visits).
				. = Missing, otherwise
Indicator of vaginal shortening after 12 weeks	CRF-10, AE log	Binary	after 12 weeks through last visit	Through the timepoint of follow-up, based on the systematic collection of open-ended adverse events as reported on the AE log with an onset start date 12 weeks after the date of surgical intervention and based on the specific complications as reported on the evaluator (blinded) follow-up CRF-10 collected at 6-weeks and in 6-month intervals through 5 years, the indicator is defined as follows:
				1 = Yes, if vaginal shortening is reported as evident (i.e. response of "AE", "SAE") on any of the complication tables as described above or on the AE log identified by the AE verbatim terms containing "vaginal shortening" (case insensitive)
				0 = No, else if subject attended at least one post-operative visit 6 months or after and complication(s) of interest specified above are reported as "Not Evident" across all attended post-operative visits. Subjects with missing responses are included as long as the subject has at least one "Not

				Evident" response (assuming low missing response rate among attended visits). . = Missing, otherwise
Reportable adverse events by system organ class (MedDRA coding)	AE log	Nominal Categorical	surgery through last visit	Through the timepoint of follow-up, based on the systematic collection of open-ended reportable adverse events as reported on the AE log with an onset start date on or after the date of surgical intervention, the adverse events will be coded following the MedDRA dictionary.
				Reportable adverse events are defined in the MOP as follows:
				- During the First Six Weeks Following Surgery: All AEs and SAEs of grade II or higher will be collected.
				- Between Six Weeks and Six Months: All AEs and SAEs that are deaths, require a hospitalization or an emergency room visit, and all AEs or SAEs of grade II or higher that are at least possibly related to the pelvis or surgery, in the opinion of the investigator, will be collected.
				- At All Remaining Visits: Only deaths and AEs or SAEs of grade II or higher that are at least possibly related to the pelvis or surgery, in the opinion of the investigator, will be collected.
				*Note: Events reported on the AE log corresponding to the following functional efficacy outcomes will be excluded: new or worsening stress urinary incontinence (MedDRA coded preferred term "stress urinary incontinence"), new or worsening urgency urinary incontinence (MedDRA coded preferred term "urge incontinence"), new or worsening fecal incontinence (MedDRA coded preferred term "faecal incontinence"), dyspareunia (MedDRA coded preferred term "dyspareunia"), and new or worsening voiding dysfunction (MedDRA coded preferred term "urinary retention") (case insensitive).
Reportable serious adverse events by system organ class (MedDRA coding)	AE log	Nominal Categorical	surgery through last visit	Through the timepoint of follow-up, based on the systematic collection of open-ended reportable adverse events as reported on the AE log with an onset start date on or after the date of surgical intervention where the

adverse events will be coded following the MedDRA dictionary and classified as a serious adverse event as defined in the MOP as any reportable adverse event that:
- results in death
- is life-threatening (places the subject at immediate risk of death from the event as it occurred)
- results in inpatient hospitalization or prolongation of existing hospitalization
- results in a persistent or significant disability/incapacity
- is another medically important condition - based upon appropriate medical judgment, may jeopardize the subject's health and may require medical or surgical intervention to prevent one of the other outcomes listed in this definition (examples of such events include allergic bronchospasm requiring intensive treatment in the emergency room or at home, blood dyscrasias or convulsions that do not result in inpatient hospitalization, or the development of drug dependency or drug abuse)
- medical or surgical intervention was necessary to preclude permanent impairment of a body function, or prevent permanent damage to a body structure, either situation suspected to be due to the use of a medical product (Devices)
A life-threatening AE is defined as any AE that in the view of the investigator places the study subject at immediate risk of death. It does not include an AE that might have caused death had it occurred in a more severe form.
A disability is defined as a substantial disruption of a person's ability to conduct normal life functions.

				*Note: Events reported on the AE log corresponding to the following functional efficacy outcomes will be excluded: new or worsening stress urinary incontinence (MedDRA coded preferred term "stress urinary incontinence"), new or worsening urgency urinary incontinence (MedDRA coded preferred term "urge incontinence"), new or worsening fecal incontinence (MedDRA coded preferred term "faecal incontinence"), dyspareunia (MedDRA coded preferred term "dyspareunia"), and new or worsening voiding dysfunction (MedDRA coded preferred term "urinary retention") (case insensitive).
Indicator of death outcome	AE log	Binary	surgery through last visit	Through the timepoint of follow-up, based on the systematic collection of open-ended reportable adverse events as reported on the AE log with an onset start date on or after the date of surgical intervention where the adverse events will be coded following the MedDRA dictionary, the indicator is defined as follows: 1 = Yes, if the outcome of death is reported on the AE log as described above 0 = No, else if subject attended the surgical intervention visit . = Missing, otherwise

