- Retreatment for prolapse (surgery or pessary), or
- 3. Any prolapse measure (Ba, C, Bp) is beyond the hymen (i.e. > 0 cm).

Bothersome vaginal bulge symptoms = positive response to Question 3 of the PFDI-20: Do you usually have a bulge or something falling out that you can see or feel in your vaginal area? and any degree of bother (i.e. any response other than "not at all" to the question "How much does this bother you?")

L.2. Secondary Outcome Measures

Secondary Aim 1 – Secondary Efficacy Outcomes: These measures will require a statistical analysis plan and will be reported in the primary outcome manuscript.

- Anatomic: POP-Q point (Aa, Ap, Ba, Bp, C) mean or median (but should be normally distributed)
 - (a) Measures postop in each group
 - (b) Proportion of participants in each group with C > -2/3 TVL
 - (c) Maximum extent of prolapse (defined as leading edge of prolapse Ba, C, Bp)

2. Functional:

- (d) Prolapse
 - (i) Patients Global Impression of Improvement (PGI-I) [49]
 - (ii) Mean overall prolapse symptoms using POPDI-6 scores (sub-scale of PFDI-20) [50]
- (e) Urinary
 - (i) Duration of postop catheterization
 - (ii) Mean UDI-6 scores (sub-scale of PFDI-20) [50]
 - (iii) De novo voiding dysfunction rates
 - (iv) De novo incontinence rates
 - 1. Stress
 - 2. Urge
 - 3. Mixed
- (f) Sexual/Body Image

- 1. Mean PISQ-IR [51] and BIPOP scales [52]
- 2. Rates of de novo dyspareunia
- (g) Bowel bowel function using CRADI-8 scores [50]
- (h) QOL
 - (i) General SF-12 scores and sub-scales [53]
 - (ii) Pelvic QOL mean PFIQ score [50]
 - (iii) Katz ADL (ref) (baseline only)
 - (iv) Functional Activity Scale (ref)
- Regret/Satisfaction:
 - (i) Regret with Decision Regret Scale (DRS-PFD) [54]
 - (j) Satisfaction with Decision Scale (SDS-PFD) [54]

Secondary Aim 2 – Safety: These measures will require a statistical analysis plan and will be reported in the primary outcome manuscript.

- Intraoperative safety: group comparisons of mean operative time, estimated blood loss, blood transfusion, intra- and postoperative complications categorized using a modification of the Dindo Classification. [55]
- 2. Adverse events mesh-related complications: mesh exposure in the vagina or mesh erosion into another organ and the classification of the intervention:
 - (a) None or non-surgical medical intervention only
 - (b) Minor or intra-office surgical intervention
 - (c) Outpatient surgery
 - (d) Inpatient surgery
- 3. Other complications possible in all arms:

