- e. Bowel function obtained at 6-month post-operative time points using CRADI-8 scores
- f. Quality of Life (QOL) measures obtained at 6-month post-operative time points including:
  - i. General SF-12 physical component and mental component scales
  - ii. Pelvic QOL as measured by PFIQ total score and three subscales (prolapse: POPIQ, urinary: UIQ, bowel: CRAIQ)
  - iii. Functional activity as measured by the Functional Activity Assessment Scale (FAS)
- g. Regret/Satisfaction:
  - i. Regret with Decision Regret Scale (DRS-PFD)
  - ii. Satisfaction with Decision Scale (SDS-PFD)
- 3. Safety and tolerability of the two treatment regimens:
  - a. Intraoperative safety measured in each of the treatment arms including:
    - i. Mean operative time
    - ii. Estimated blood loss
    - iii. Proportion of participants with blood transfusion
    - iv. Intra- and post-operative complications categorized using a modification of the Dindo Classification.
  - b. Risk of adverse events on the two treatment arms as measured by proportion of participants with any of the following events:
    - i. Mesh related complications: mesh exposure in the vagina or mesh erosion into another organ; note that level of complication will be characterized into based on the following response classification schema: (a) None or nonsurgical medical intervention only; (b) Minor or intra-office surgical intervention; (c) Outpatient surgery; (d) Inpatient surgery
    - Rates of pain captured from the modified Surgical Pain Scale (SPS), pain medication use (during 24 hours prior to completion of the SPS Assessment), and Body Part Pain Scales (BPPS) assessment.
    - iii. Pelvic infection
      - 1. Risk of perioperative infections
      - 2. Risk of urinary tract infections
      - 3. Vaginal infections with flora uncommon to the vaginal canal

- iv. Risk of any of De novo vaginal bleeding, atypical vaginal discharge, fistula formation, neuromuscular problems (including groin and leg pain)
- v. Need for subsequent procedures- Any surgical or non-surgical treatment for pelvic floor disorders (including urinary incontinence, voiding dysfunction, defecatory dysfunction or fecal incontinence, recurrent prolapse, and dyspareunia/pelvic pain).
- vi. Risk of vaginal scarring defined as: De novo vaginal scar requiring medical or surgical intervention, or adversely affecting quality of life.
- vii. Risk of Vaginal shortening, de novo dyspareunia, and

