## **10.2** Safety and Tolerability Variables

Variable	CRF Source	Туре	Timepoint(s)	Definition
Secondary Safety and Toler	ability Outcon	mes		
Indicator of prolapse mesh exposure in the anterior vagina	CRF-8, CRF- 10/12, AE log	Binary	Post-surgery through last visit	
 
Through the timepoint of follow-up, the indicator is defined as follows:
 
1 = Yes, if mesh exposure in vagina is reported as evident (i.e. response of "AE", "SAE") and Anterior=Yes and Description of Management of Mesh Exposure indicates the mesh was "from/for Prolapse Surgery" (case insensitive) on any of the complication tables as described above
 
0 = No, else if subject attended at least one post-operative visit 6 weeks or after and complication(s) of interest specified above are reported as "Not Evident" across all attended post-operative visits. Subjects with missing responses are included as long as the subject has at least one "Not Evident" response (assuming low missing response rate among attended visits).
 
. = Missing, otherwise
 

Indicator of prolapse mesh exposure in the posterior vagina	CRF-8, CRF- 10/12, AE log	Binary	Post-surgery through last visit	
 
Through the timepoint of follow-up, the indicator is defined as follows:
 
1 = Yes, if mesh exposure in vagina is reported as evident (i.e. response of "AE", "SAE") and Posterior=Yes and Description of Management of Mesh Exposure indicates the mesh was "from/for Prolapse Surgery" (case insensitive) on any of the complication tables as described above
 
0 = No, else if subject attended at least one post-operative visit 6 weeks or after and complication(s) of interest specified above are reported as "Not Evident" across all attended post-operative visits. Subjects with missing responses are
 

				<pre>included as long as the subject has at least one "Not Evident" response (assuming low missing response rate among attended visits).</pre> . = Missing, otherwise
exposure in the distal (lower half/introitus) vagina	CRF-8, CRF- 10/12, AE log	Binary	Post-surgery through last visit	Through the timepoint of follow-up, the indicator is defined as follows:         1 = Yes, if mesh exposure in vagina is reported as evident (i.e. response of "AE", "SAE") and distal (lower half/introitus)=Yes and Description of Management of Mesh Exposure indicates the mesh was "from/for Prolapse Surgery" (case insensitive)         on any of the complication tables as described above

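### SAP 10.2 defines neither the promised any-site mesh exposure (or exposure-or-erosion) proportion nor its intervention class, and its site rows code some unexposed sites as missing instead of No

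*SAP*

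**What the plan says.** Protocol L.2 (Secondary Aim 2, Safety) lists "mesh exposure in the vagina or mesh erosion into another organ and the classification of the intervention". The four classes are: (a) none or non-surgical, (b) minor or office, (c) outpatient surgery, (d) inpatient surgery. The measures under that aim are to be reported in the primary outcome manuscript.

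SAP 3.2 repeats the promise at the level of the woman. Risk of adverse events is "as measured by proportion of participants with any of the following events", and the first item is "Mesh related complications: mesh exposure in the vagina or mesh erosion into another organ; note that level of complication will be characterized" on the same four classes.

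SAP 10.2 then defines the variables. For prolapse mesh there is an "Indicator of prolapse mesh exposure in the anterior vagina", an "Indicator of prolapse mesh exposure in the posterior vagina", and matching rows for the distal vagina and the apex. The same four rows are repeated for sling mesh. Each mesh type also has one erosion row. The codes in an exposure row are:

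- **1**: vaginal mesh exposure is recorded as AE or SAE, the site is marked *Yes* and the mesh is of the right type. The anterior row reads "and Anterior=Yes and Description of Management of Mesh Exposure indicates the mesh was" from prolapse surgery.
- **0**: the woman attended at least one visit from 6 weeks on, and the "complication(s) of interest specified above are reported as" *Not Evident* at all attended visits. The only stated exception is for missing responses.
- **Missing**: everything else.

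**The concern.** Mesh erosion and exposure are named in the safety aim, and they are the events on which transvaginal mesh (TVM) and sacral colpopexy (SC) most need comparing. A reader of the primary manuscript will want two figures by arm: how many women had a mesh complication, and how many needed surgery for it. SAP 3.2 promises both, but 10.2 gives neither a derivation. If the headline rate is left undefined, several choices stay open until after unmasking: which sites count, whether erosion counts, and who is in the denominator. The 0 rule adds a separate fault, because it can remove women from a site's denominator when they plainly had no exposure at that site.

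**Working it through.** The plan states no figure for this outcome, so there is nothing to reproduce. The check compares the promise with the definitions, applies the coding rule to test cases, and sizes the effect.

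**1. Promise against definition**

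| Promised (Protocol L.2, SAP 3.2) | Defined in SAP 10.2 |
|---|---|
| Any vaginal mesh exposure, per woman | No row; four site rows per mesh type |
| Exposure or erosion, per woman | No row |
| Erosion into another organ | Yes, but the prolapse-mesh row is limited to Uphold Lite recipients |
| Intervention class (a) to (d) | No row; the management description serves only to tell prolapse mesh from sling mesh |

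The nearest severity variable is the maximum Dindo score, which pools all complications and is not specific to mesh. A note under the sling erosion row refers back to an indicator of hysteropexy mesh exposure that is not in the table. An overall exposure row may have been lost when the table was adapted.

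**2. The coding rule applied literally** (prolapse-mesh rows)

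| Woman | Anterior | Posterior | Distal | Apex |
|---|---|---|---|---|
| Never exposed | 0 | 0 | 0 | 0 |
| Anterior only | 1 | missing | missing | missing |
| Anterior and distal | 1 | missing | 1 | missing |
| Sling mesh only | missing | missing | missing | missing |

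The last three women have an AE for mesh exposure in the vagina. They therefore fail the *Not Evident* condition, and the missing-response exception does not cover them.

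**3. Size of the denominator effect**

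Let n be the women in the arm, a those exposed at the site, and e those exposed only elsewhere. The literal rate is a/(n − e); the correct rate is a/n. I take n = 121 (the planned arm size, Protocol M.1) and assume that about half of exposed women are anterior only and the rest are at one other site. The low exposure rate, 2.6%, is from a series of 115 women in Protocol B.1.c. The high one, 15%, is the threshold in Protocol N.1 for erosion needing operating-room removal, used here only as an upper bound.

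| Assumed rate | Exposed | Literal anterior | Full denominator | Difference (points) |
|---|---|---|---|---|
| 2.6% | 3 | 2/120 = 1.67% | 2/121 = 1.65% | 0.01 |
| 5% | 6 | 3/118 = 2.54% | 3/121 = 2.48% | 0.06 |
| 10% | 12 | 6/115 = 5.22% | 6/121 = 4.96% | 0.26 |
| 15% | 18 | 9/112 = 8.04% | 9/121 = 7.44% | 0.60 |

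Differences are taken before rounding.

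**4. Why the rows cannot be summed**

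Suppose 11 of 115 TVM women are exposed (9.6%): 6 at the apex only, 3 anterior only, 2 at both. The figure of 115 is about 95% of 121, as SAP 6 expects for that arm. The split is invented for illustration.

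- Anterior: (3 + 2)/(115 − 6) = 5/109 = 4.6%
- Apex: (6 + 2)/(115 − 3) = 8/112 = 7.1%
- Posterior and distal: 0/(115 − 11) = 0/104 each

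The rows hold 5 + 8 = 13 positives for 11 women, on three different denominators, and no row shows 9.6%.

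**The case against.** **The 0 code can be read site by site.** On that reading, the complication of interest in each row is the whole compound: exposure, at this site, from this mesh. A woman exposed only at the apex would then be 0 in the anterior row. SAP 7.5 also requires every exposure or erosion to be attributed to prolapse surgery or sling, so the two are meant to be kept apart. This reading is possible. But *Not Evident* is the alternative to AE or SAE for mesh exposure in the vagina as a whole, while sites are marked *Yes*, so the literal reading is the more natural one. If the compound was meant, one clause would settle it.

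**A reader might infer that the mesh-safety outcome is never produced.** The documents do not support that. Any exposed woman has a 1 in at least one site row, so her any-site status is the maximum of the four. Erosion rows exist. All AEs are tabulated by preferred term (SAP 10.5), and the table shells are in a separate document (SAP 14) that may well include an overall row. None of these, however, defines the promised variable. The AE tables carry no intervention class, and reportable AEs are limited to grade II or higher. The maximum also does not help a woman with sling exposure only: all four of her rows are missing, so her any-site status is missing when it should be 0.

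**A reader might infer that the missing codes cause the absent overall rate, or that four rows cost power.** The first does not follow: the overall rate is absent because no row defines it. On the second, SAP 7.7 makes secondary p-values and intervals descriptive and not to be judged for significance, so power per row bears on no decision in the plan.

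**Conclusion.** The point stands as a gap in definition plus a small coding error. SAP 3.2 and Protocol L.2 promise a participant-level proportion and a four-level intervention class; SAP 10.2 defines neither. The 0 rule on its natural reading gives wrong site denominators. In the illustration that moves a site rate by 0.01 to 0.60 percentage points, which would not change a conclusion. It rests on 121 women per arm, the assumed exposure rates and an even split between two sites.

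The undefined headline rate matters more than the denominators, because the site rows overlap and cannot be added. One related limit affects any combined indicator: the prolapse-mesh erosion row covers only Uphold Lite recipients, so erosion of SC mesh is left out of it. The sling erosion row even counts visceral erosion as sling erosion in women with a sling who did not receive Uphold Lite, on the ground that they have no other mesh. That is untrue of women who had SC.

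The documents cannot show what the table shells contain or whether the intervention class sits in a codable field.

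**What to change.** In SAP 10.2:

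1. Add any prolapse-mesh vaginal exposure (1 if any site row is 1), and the promised exposure-or-erosion indicator. Report both by arm with a risk difference and 95% CI, using the SAP 10.3 methods, as descriptive safety outcomes.
2. Add the highest intervention class (a) to (d) per woman, tabulated by arm, from the classification that Protocol I and L.2 say is assessed.
3. Add a clause coding a site row 0 when exposure is reported only at another site or only from the other mesh type, so that a woman with only sling exposure is 0 on the prolapse-mesh rows and on the any-exposure indicator.
4. Remove the Uphold Lite restriction from the prolapse-mesh erosion row, so that the combined indicator is comparable between TVM and SC, and bring the sling erosion row into line.
5. Keep the site rows as description, and correct the reference to the hysteropexy exposure indicator.

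The cost is SAP wording and a little extra derivation. Exposure and site are already recorded. The CRFs are not in the documents, so confirm first that the intervention class was captured as a code; if only the free-text description exists, a masked classification of the few exposed women would be needed.
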